2.4. Bone Histomorphometry Results from Study BA058-05-003

In Study [BA058-05-003](#), a subset of subjects at selected centers was asked to undergo a bone biopsy ([Moreira, 2017](#)). Biopsies were obtained after the subjects had received between 12 and 18 months of treatment and were obtained primarily to assess safety. Qualitative histological analysis of biopsies from abaloparatide-treated subjects revealed normal bone microarchitecture without evidence of adverse effects on mineralization or on the formation of normal lamellar bone. There were no bone marrow abnormalities or marrow fibrosis, nor was there presence of excess osteoid or woven bone. There were few significant differences among the three treatment groups in a standard panel of static and dynamic histomorphometric indices. The mineral apposition rate was higher in the teriparatide-treated group than in the placebo-treated group. The eroded surface was lower in the abaloparatide-treated group than in the placebo-treated group. Cortical porosity was higher in both the abaloparatide- and the teriparatide-treated groups than in the placebo-treated group.

2.5. Study Rationale

The purpose of this study is to assess the early effects of abaloparatide in postmenopausal women with osteoporosis using tissue-based indices of bone metabolism obtained by iliac crest bone biopsy after quadruple tetracycline labeling and to relate these indices to biochemical markers of bone turnover. All four bone envelopes (cancellous, endocortical, intracortical, and periosteal) will be examined.

2.6. Dose Rationale

The approved dose of abaloparatide in the US for the treatment of postmenopausal women at a risk for fracture is 80 µg per day.

3. STUDY OBJECTIVES AND ENDPOINTS

3.1. Objectives

1. Demonstrate the early effects of abaloparatide on tissue-based indices of bone formation and resorption
2. Assess the degree to which increased bone formation is achieved by modeling, remodeling, and overflow bone formation
3. Relate the early indices of tissue-based bone formation and bone resorption to those measured using biochemical markers of bone turnover

3.2. Endpoints

- Change from baseline to 3 months in dynamic indices of bone formation in the relevant bone envelopes (cancellous, endocortical, intracortical, and periosteal)
 - Mineralizing surface (MS/BS)
 - Mineral apposition rate (MAR)
 - Bone formation rate (BFR/BS)
- Structural indices in the relevant bone envelopes at Month 3
 - Cortical porosity (Ct.Po/Ct.Ar)
- Static indices in the relevant bone envelopes at Month 3
 - Osteoid volume (OV/BV)
 - Osteoid surface (OS/BS)
 - Osteoid thickness (O.Th)
 - Wall thickness (W.Th)
 - Eroded surface (ES/BS)
- Change from baseline to 3 months in special histomorphometric variables in the relevant bone envelopes
 - Remodeling, modeling, and overflow modeling-based formation (RmF/BS, MF/BS, oMF/BS)
- Change in serum procollagen type I N-terminal propeptide (s-PINP) and carboxy-terminal cross-linking telopeptide of type I collagen (s-CTX) from baseline to 1 and 3 months
- Correlations of tissue-based indices of bone formation and bone resorption with s-PINP and s-CTX
- Overall safety and tolerability of abaloparatide in postmenopausal women with osteoporosis.

[figure not shown]
4. STUDY DESIGN

4.1. Description of the Study Design

This is an open-label, single-arm, multicenter study enrolling approximately 25 postmenopausal women with osteoporosis at approximately 5 study centers. The study is designed to measure the early effects of abaloparatide on tissue-based bone formation and resorption variables based on samples obtained by iliac crest bone biopsy after fluorochrome labeling. The study will consist of a Screening Period (up to 1 month), a Pretreatment Period (approximately 1 month), a Treatment Period (3 months), and a Month 4 visit one month after the last dose of study medication. Biopsies are to be obtained at 3 months of treatment for the following reasons:

- This is the optimal time for changes in biochemical markers of bone turnover to predict changes in BMD after 18 months of treatment with abaloparatide (Radius, Data on file)
- Longer periods of time increase the risk that the initial set of labels will be resorbed, which would seriously confound the results
- Comparisons to the 3-month results for teriparatide from the AVA Osteoporosis Study will be possible (Dempster, 2016)

Figure 1: BA058-05-020 Study Design, Including Schematic of Bone Biopsy Labeling Procedure

Full details of the protocol required assessments can be found in the Schedule of Assessments and Procedures ([Section 7.2.1](#)).

There will be a sub-study at selected sites to collect pQCT data and extend an additional 3 months of study drug administration for a total of 6 months of treatment.

Details of the schedule of measurements, endpoints and statistical analysis methods for the sub-study will be described in a separate document.

5. SELECTION OF STUDY POPULATION

5.1. Inclusion Criteria

Subjects must meet all of the following criteria to be eligible to participate in this study:

1. The subject is a healthy ambulatory postmenopausal female from 50 to 85 years of age (inclusive) with osteoporosis.
2. The subject has been postmenopausal for at least 5 years. Postmenopausal status will be established by a history of amenorrhea for at least 5 years and by an elevated follicle-stimulating hormone (FSH) value of ≥ 30 IU/L.
3. The subject has a BMD T-score ≤ -2.5 at the lumbar spine (L1-L4) or hip (femoral neck or total hip) by DXA *or* lumbar spine or hip BMD T-score ≤ -2.0 with a history of low trauma vertebral, forearm, humerus, sacral, pelvic, hip, femoral, or tibial fracture sustained within 5 years prior to enrollment. These fractures must be documented by radiograph or hospital report.
4. The subject is in good general health as determined by medical history and physical examination (including vital signs), has a body mass index (BMI) of 18.5 to 33, inclusive, and is without evidence of clinically significant abnormality in the opinion of the Investigator.
5. The subject has serum calcium (albumin-corrected), PTH (1-84), phosphorus, and alkaline phosphatase levels all within the normal range during the Screening Period. Any subject with an elevated alkaline phosphatase value, and who meets all other entry criteria, is required to have a normal bone-specific alkaline phosphatase result to be enrolled.
6. The subject has serum 25-hydroxyvitamin D values ≥ 20 ng/mL and within the normal range. Subjects with serum 25-hydroxyvitamin D levels < 20 ng/ml may be treated with vitamin D3 and re-tested once.
7. The subject's resting 12-lead electrocardiogram (ECG) obtained during screening shows no clinically significant abnormality.
8. The subject has read, understood, and signed the written informed consent form.

5.2. Exclusion Criteria

Subjects with any of the following characteristics are not eligible to participate in the study:

General exclusion criteria

1. Presence of abnormalities of the lumbar spine that would prohibit assessment of lumbar spine BMD, defined as having at least 2 radiologically evaluable vertebrae within L1-L4.
2. Unevaluable hip BMD or subjects who have undergone bilateral hip replacement (unilateral hip replacement is acceptable).
3. History of bone disorders (eg, Paget's disease) other than postmenopausal osteoporosis.
4. Clinically significant abnormality of serum hemoglobin, hematocrit, white blood cells (WBC) and platelets, coagulation, or usual serum chemistry: electrolytes, renal function, liver function and serum proteins.
5. Unexplained elevation of serum alkaline phosphatase.
6. History of radiotherapy (radiation therapy), other than radioiodine.
7. History of bleeding disorder that would preclude a bone biopsy, in the opinion of the Investigator.
8. History of chronic or recurrent renal, hepatic, pulmonary, allergic, cardiovascular, gastrointestinal, endocrine, central nervous system, hematologic or metabolic diseases, or immunologic, emotional and/or psychiatric disturbances to a degree that would interfere with the interpretation of study data or compromise the safety of the subject.
9. History of Cushing's disease, hyperthyroidism, hypo- or hyperparathyroidism, or malabsorptive syndromes within the past year.
10. History of significantly impaired renal function (serum creatinine > 177 $\mu\text{mol/L}$ or > 2.0 mg/dL). If the serum creatinine is > 1.5 and \leq 2.0 mg/dL, the calculated creatinine clearance (Cockcroft-Gault) must be \geq 30 mL/min.
11. History of any cancer within the past 5 years (other than basal cell or squamous cell cancer of the skin).
12. History of osteosarcoma at any time or a history of hereditary disorders which could predispose the subject to osteosarcoma.
13. History of nephrolithiasis or urolithiasis within the past five years.
14. Subjects known to be positive for hepatitis B, hepatitis C, human immunodeficiency virus infection (HIV-1 or HIV-2). Testing is not required in the absence of clinical signs and symptoms suggestive of HIV infection or acute or chronic hepatitis.

Medication-related exclusion criteria

15. Known history of hypersensitivity to any of the test materials, related compounds, or tetracyclines.
16. Prior treatment with PTH or PTHrP drugs, including abaloparatide.
17. Prior treatment with IV bisphosphonates at any time or oral bisphosphonates within the past three years. Subjects who had received a short course of oral bisphosphonate therapy (3 months or less) may be enrolled as long as the treatment occurred 6 or more months prior to enrollment.
18. Treatment with fluoride or strontium in the five years prior to the Screening Period, or prior treatment with gallium nitrate, or with any unapproved bone-acting investigational agents at any time.
19. Treatment with calcitonin, SERMs (such as raloxifene or tamoxifen), or tibolone, within the 6 months prior to the Screening Period. Estrogens administered as hormone replacement therapy with or without progestins are not exclusionary.
20. Treatment with anticonvulsants that affect vitamin D metabolism (phenobarbital, phenytoin, carbamazepine or primidone) or with chronic heparin within the 6 months prior to the Screening Period.
21. Prior treatment with denosumab.
22. Daily treatment with oral, intranasal or inhaled corticosteroids within the 12 months prior to the Screening Period. Occasional use of corticosteroids (for seasonal allergies or asthma) is not exclusionary.
23. Prior treatment with anabolic steroids or calcineurin inhibitors (cyclosporin, tacrolimus).
24. Exposure to an investigational drug within the 12 months prior to the Screening Period.

Lifestyle-related exclusion criteria

25. Abnormal nutritional status (abnormal diets, excessive or unusual vitamin or herbal intakes, malabsorption, significant recent weight change), vitamin D intake of $\geq 4,000$ IU/day or vitamin A intake of $\geq 10,000$ IU/day.
26. Subject is known to abuse alcohol or use illegal drugs within 12 months of the Screening Period.

5.3. Participant Withdrawal or Termination

5.3.1. Reasons for Withdrawal or Termination

Subjects will be informed that they have the right to withdraw from the study at any time for any reason without prejudice to their medical care.

The Investigator must withdraw subjects from the study for the following reasons:

- Hypercalcemia as described in [Section 5.7.1](#);
- Severe hypersensitivity to abaloparatide;

- Refusal of treatment;
- Inability to complete study procedures;
- Lost to follow-up.

The Investigator also has the right to withdraw subjects from the study for any of the following reasons:

- Serious adverse events (as described in [Section 8.1.2](#));
- A complex of adverse events which, in the judgment of the Investigator, justifies treatment cessation;
- Serious intercurrent illness;
- Non-compliance;
- Protocol violations;
- Administrative reasons.

Subjects will be offered the opportunity to discontinue from the study for the following reasons after site consultation with the Study Medical Monitor:

- Incident vertebral or nonvertebral fragility fracture

Should a subject who experiences a clinical vertebral or nonvertebral fragility fracture choose to remain in the study, she will be asked to sign an additional Informed Consent Form further explaining the potential risks and benefits of remaining in the study.

5.3.2. Handling of Participant Withdrawals or Terminations

If a subject is withdrawn or discontinued from the study, the reason for withdrawal from the study is to be recorded in the source documents and on the case report form. All subjects withdrawn prior to completing the study should be encouraged to complete study procedures scheduled for the Month 3/Early Termination visit and to return in one month for a follow-up visit. The Sponsor Medical Monitor will decide if the tetracycline labeling procedure and bone biopsy will be performed as part of the Early Termination visit. All adverse events should be followed as described in [Section 8](#). Subjects who discontinue or are withdrawn from the study may be replaced.

5.4. Concomitant Medications

Vitamin D supplements are required to be administered daily from the Pretreatment Period until the end of the Treatment Period. Calcium will also be administered daily, with the exception of the days of administration of demeclocycline and tetracycline where calcium administration will be withheld. The doses and schedule of calcium and vitamin D supplements ([Section 7.2.5](#)) should be adhered to and not be changed other than for medical necessity. The supplements should be taken in the evening with or without food or as otherwise instructed by the Investigator. Calcium (500–1000 mg) and vitamin D (400–800 IU) supplements will be sourced locally by the site and provided to the subjects at the expense of the Sponsor.

Two different fluorochromes (demeclocycline HCl and tetracycline HCl) are used for the pre-treatment and on-treatment labels. Instructions for administration of fluorochromes is detailed in [Section 7.2.6](#) and [Section 7.2.9](#).

For any required concomitant medication, such as statins or antihypertensives, the subject must be on a stable dose at study entry and every effort should be made to maintain a stable dose during study participation.

The occasional use of over-the-counter medications at approved doses (eg, ibuprofen or acetaminophen) for headache or minor discomfort is allowed. These are to be recorded on the appropriate eCRF. Subjects should not take any other medications, including over-the-counter medications, herbal medications, or mega-doses of vitamins during the study without prior approval of the Investigator.

If it becomes necessary for a subject to take any other medication during the study, the specific medication(s) and indication(s) must be discussed with the Investigator. All concomitant medications taken during the course of the study must be recorded in the subject's medical record or source document and transcribed into the eCRF.

5.5. Prohibited Medications

Please refer to [Section 5.2](#) for medication-related exclusion criteria.

Subjects cannot take any medications, including over-the-counter, non-prescription medication, with the exception of those noted in [Section 5.4](#), within 72 hours prior to dosing on Day 1. In addition, subjects are ineligible for the study if they have an abnormal nutritional status (abnormal diets, excessive or unusual vitamin or herbal intakes, malabsorption).

Occasional short-term (≤ 1 week) use of inhaled corticosteroids for seasonal allergies or asthma is not prohibited. Subjects who require chronic treatment with either an anticonvulsant (phenobarbital, phenytoin, carbamazepine or primidone), or with heparin will be discontinued.

5.6. Premature Termination or Suspension of Study

This study may be temporarily suspended or prematurely terminated if there is sufficient reasonable cause. Written notification documenting the reason for study suspension or termination will be provided by the suspending or terminating party to the Principal Investigator (PI), and regulatory authorities. If the study is prematurely terminated or suspended, the PI will promptly inform the Institutional Review Board (IRB) and will provide the reason(s) for the termination or suspension.

Circumstances that may warrant termination or suspension include, but are not limited to:

- Determination of unexpected, significant, or unacceptable risk to participants
- Insufficient compliance with protocol requirements
- Data that are not sufficiently complete and/or evaluable
- Decision of Sponsor

The study may resume once concerns about safety, protocol compliance, or data quality are addressed and satisfy the Sponsor, IRB, and/or Regulatory Agencies, if applicable.

5.7. Temporary Suspension of Treatment

The Investigator has the right to suspend treatment with study medication for up to 7 cumulative days, without withdrawal of the subject from the study. Reasons for temporary suspension of treatment may include a medical reason unrelated to an adverse event (eg, a planned procedure), or important social or administrative events. The reason for the suspension of treatment is to be documented in the eCRF and in source documents.

When treatment is restarted, the subject should resume treatment with the next scheduled dose and continue until the scheduled End-of-Treatment.

Subjects who develop hypercalcemia during the study are to have treatment with calcium and vitamin D temporarily suspended as described below.

5.7.1. Treatment Algorithm in Subjects Who Develop Hypercalcemia

For any predose serum calcium (albumin-corrected) value which is ≥ 0.3 to 1.0 mg/dL, corresponding to ≥ 0.08 to 0.25 mmol/L, above the upper limit of normal (ULN) (inclusive), the Investigator will confirm hypercalcemia by drawing a new serum sample as soon as possible after the result is received.

If a subject's predose serum calcium is elevated on repeated testing, calcium and vitamin D supplementation should be withheld. If the subject's serum calcium remains elevated 1 to 2 weeks after calcium and vitamin D supplementation is withheld, dosing of study medication should be stopped. Treatment can be restarted if other causes of hypercalcemia are excluded after consultation with the Sponsor. Treatment with study medication should not be suspended for greater than 7 days.

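### Protocol 5.7.1 gives no hypercalcaemia withdrawal criterion and no prompt drug hold or timed retest above ULN + 1.0 mg/dL; separately, the SAP drops a related adverse-event summary

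*Protocol*

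**What the plan says.** **Withdrawal (Protocol 5.3.1).** One list opens "The Investigator must withdraw subjects from the study for the following reasons", and its first item is hypercalcaemia, defined by reference to 5.7.1. A second, discretionary list opens "The Investigator also has the right to withdraw subjects from the study for any of the following reasons" and includes serious adverse events and a complex of adverse events.

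**Suspension (Protocol 5.7).** "The Investigator has the right to suspend treatment with study medication for up to 7 cumulative days, without withdrawal of the subject from the study". The reasons given are examples, not a closed list. On hypercalcaemia: "Subjects who develop hypercalcemia during the study are to have treatment with calcium and vitamin D temporarily suspended as described below".

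**Algorithm (Protocol 5.7.1).** For a predose albumin-corrected calcium between 0.3 and 1.0 mg/dL "above the upper limit of normal (ULN) (inclusive), the Investigator will confirm hypercalcemia by drawing a new serum sample", as soon as possible once the result is known. If the repeat is also raised, calcium and vitamin D are withheld. If calcium is still raised 1 to 2 weeks after that, "dosing of study medication should be stopped. Treatment can be restarted if other causes of hypercalcemia are excluded after consultation with the Sponsor". Suspension of study drug is limited to 7 days.

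**Laboratory follow-up (Protocol 7.5.1).** Abnormal results are to be repeated and followed until they are normal or explained. No time limit is set.

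**Analysis.** Protocol 9.4.4 specifies a count and percentage of subjects with treatment-emergent events related to hypercalcaemia and hypercalciuria. SAP 4.7.1 lists these further adverse-event tables: common, severe, serious, leading to drug withdrawal, drug-related and non-treatment-emergent. The calcium-related summary is not among them. SAP Section 5 lists five changes from the protocol, and this is not one of them.

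**The concern.** A mandatory withdrawal rule refers to a section that never mentions withdrawal, so sites have to work out for themselves when it applies. Two Investigators facing the same calcium course could reach different answers.

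The timed retest has an upper bound and there is no tier above it. Followed literally, the highest calcium values get no faster drug hold, and a less clearly timed retest, than moderate ones. A prompt hold then depends on each Investigator's discretion.

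The SAP point is smaller and separate. Calcium-related events are the only event-specific treatment-emergent summary that 9.4.4 names. SAP Section 1 undertakes to identify substantial differences from the protocol, yet this analysis disappears without comment. Neither document lists the preferred terms that would count.

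**Working it through.** **Unit check on the plan's own thresholds.** The protocol equates 1.0 mg/dL with 0.25 mmol/L, a factor of 0.25. Then 0.3 × 0.25 = 0.075, which rounds to the stated 0.08. The band is consistent: ULN + 0.3 to ULN + 1.0 mg/dL.

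**Is there a withdrawal criterion?** 5.3.1 requires one and refers to 5.7.1. The steps in 5.7.1 are retest, withhold supplements, stop drug, possible restart, and a 7-day limit on suspension. None says that the subject is withdrawn, and no consequence is given for passing the limit. Restart requires other causes to be excluded and the Sponsor consulted, but no calcium level. Reading the limit with the 7 cumulative days in 5.7 suggests withdrawal when dosing cannot resume in time. That is an inference, and the text does not say whether the two 7-day figures are one allowance.

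**What is mandated at each level?**

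| | ULN + 0.3 to 1.0 mg/dL | Above ULN + 1.0 mg/dL |
|---|---|---|
| Retest | As soon as possible (5.7.1) | Repeat under 7.5.1, untimed |
| Supplements | Withheld (5.7, 5.7.1) | Withheld (5.7; second paragraph of 5.7.1 has no upper bound) |
| Mandated drug stop | If still raised 1 to 2 weeks later | At best the same 1 to 2 week path |
| Discretionary drug hold | Up to 7 cumulative days (5.7) | Same |

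**Doses between withholding supplements and the mandated stop.** Inputs: 80 µg once daily (Protocol 6.4); a 30-day month (7.2), so 3 × 30 = 90 days in the main study and 6 × 30 = 180 days under the addendum; recheck at 7 to 14 days (5.7.1).

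No discretionary hold:
- 7 doses: 7 × 80 = 560 µg; 7/90 = 7.8%; 7/180 = 3.9%
- 14 doses: 14 × 80 = 1120 µg; 14/90 = 15.6%; 14/180 = 7.8%

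Full 7-day hold under 5.7, starting the day supplements are withheld:
- recheck at day 7: 7 − 7 = 0 doses
- recheck at day 14: 14 − 7 = 7 doses = 560 µg; 7/90 = 7.8%; 7/180 = 3.9%

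Doses given while the repeat result is awaited are extra.

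**How often could the rule be reached?** In the main study, scheduled predose chemistry falls on Day 1, Month 1 and Month 3. The Month 3 visit is also the last dose, so only Month 1 is an on-treatment sample with dosing still to come. Under the addendum there are two such samples, Months 1 and 3. Neither document gives the frequency of calcium more than 1.0 mg/dL above ULN, so no number of subjects can be estimated.

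**SAP comparison.** Neither hypercalcaemia nor hypercalciuria is mentioned in any section of the SAP. Individual terms would still appear in the system organ class and preferred term tables (4.7.1), and calcium in the shift tables, including worst post-baseline value (4.7.3). Protocol Table 2 has no urinary calcium test, so hypercalciuria terms could arise only from unscheduled testing.

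**The case against.** The best reply is that more of the mandatory text reaches the highest values than first appears. The band limits only the confirmatory-sample sentence; the steps after it have no ceiling, and 5.7 suspends supplements for any hypercalcaemia. Repeat testing under 7.5.1 also applies, and the Investigator may hold drug or withdraw the subject. This stands, and it narrows the point: what is missing is a mandatory prompt drug hold and a timed retest, not every safeguard or route to act.

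Several further arguments have some force:

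- The 7-day limits already suggest a withdrawal rule. They do, but a mandatory rule should be stated rather than inferred.
- An Investigator who holds drug can recheck on day 7, within the allowance. True; the hold falls short only when the recheck is later, which the text allows up to day 14.
- The 7 to 14 doses describe the ordinary stepwise path, not something peculiar to values above 1.0 mg/dL. Correct; they show how long dosing may continue at the highest values because no faster path exists.
- Nothing in the documents independently justifies ULN + 1.0 mg/dL as the level for an immediate hold. Correct; it is used because the protocol's own band ends there.
- Risk is limited by entry criteria requiring normal calcium and PTH, and by use of the approved dose. This bears on frequency, not on what to do when a high value occurs.
- In about 25 subjects, a reader could count the events from the remaining tables and listings. Largely so, which is why the SAP part is small; the omission is still undeclared.

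The Medical Monitoring Plan, Laboratory Manual and Investigator's Brochure were not available and may contain calcium alerts. Those might close the practical gap, but would not supply the criterion that 5.3.1 places in 5.7.1.

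**Conclusion.** The concern holds and should be fixed. Section 5.7.1 lacks the withdrawal criterion that 5.3.1 sends the reader to find, and above ULN + 1.0 mg/dL no prompt drug hold or timed retest is mandated. Dosing may continue for 7 to 14 doses after supplements are withheld if discretion is not used, or 0 to 7 if the full 7-day hold is used from the same day. These are bounds, assuming once-daily dosing without missed doses. The number of subjects affected is unknown. The missing SAP summary is an undeclared departure with a modest consequence: one grouped safety count. The primary endpoint is not affected. The finding concerns the protocol and SAP text only.

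**What to change.** **Protocol 5.7.1.** Add a tier: for predose albumin-corrected calcium more than 1.0 mg/dL (0.25 mmol/L) above ULN, hold study drug, calcium and vitamin D at once, and draw a new sample as soon as possible after the result arrives. Simply deleting the upper bound of the present band is not enough, because the 1 to 2 week path to a drug stop would remain. State that a subject whose dosing cannot resume within 7 days is withdrawn under 5.3.1, and whether this hold counts towards the 7 cumulative days in 5.7.

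**SAP 4.7.1.** Restore the hypercalcaemia and hypercalciuria summary with a preferred-term list, or declare and justify its removal in Section 5.

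**Cost.** A short protocol clarification; occasional holds of at most 7 of 90 doses, a length 5.7 already permits without withdrawal; and one table from data already collected. Loss of a subject can be made good, since 5.3.2 says "Subjects who discontinue or are withdrawn from the study may be replaced". If dosing has finished, the protocol wording is a lesson for later studies, but the SAP part can still be put right, or the omission explained in the clinical study report.
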